### 12.2.2 Data security, access and back-up

Physical access to the data centre is logged and limited to authorised personnel using badge authentication. On a regular basis, vulnerability testing is performed to reduce potential exposure. Remote access to servers is limited to authorised personnel. Connections to servers are encrypted using SSH. System logs are stored in a dedicated centralised system for audit purposes. The internal HUG network is protected by multiple firewalls, proxy, reverse-proxy and anti-virus solutions. Web servers operate under SSL (HTTPS) certifications, ensuring Web connections are encrypted and secure.

All study information collected by study personnel will be entered into an electronic database (REDCap). Access to the database will be restricted by unique password and username and back-up copies made and stored separately. Only people part of the investigation team, the sponsor team, the affiliated reviewers or auditors, as well as inspection authorities are given access to data.

Personal accounts are granted individually for each person. Identification is made by a personnel ID and a password. Failure to provide the correct password after a limited number of attempts automatically deactivates the faulty account (protection against non-authorised attacks).

Only institutional e-mail addresses will be accepted for any communication of sensitive data regarding account creation and management. Pen-Tests (simulation of malware attacks) are regularly performed, and measures taken whenever necessary.

### 12.2.3 Analysis and archiving

Data will be collected directly by the subjects' parents (through REDCap questionnaire) or via study nurses and investigators. A dedicated CDMS project will be created for the eCRF (using RedCAP®). This eCRF will reflect the visit plan and all subject-related data to be collected, as described by the study protocol. CRF data are of different data-types, mainly numeric values, encoded values, text descriptions, etc. Coding, catalogues and multi-choice values will be preferably used as opposed to free-text values. Automatic score calculations will be performed whenever appropriate (e.g. POEM and SCORAD severity scores). The eCRF will ensure high data quality control by applying logical and managerial controls over data capture in order to ensure consistency, completeness and coherence of data.

A more exhaustive and detailed Data Management Plan will be generated and applied during the whole data management process (until data are archived), after the sponsor-investigator has obtained the grant and contracted UIC.

The investigation team will enter the data interactively in the CDMS by means of its interactive graphical

interface. Data will be edited and viewed by the investigation personnel based on the role of each participant.

All modifications to the eCRF during the study conduct will be tracked and dealt with consequently (version numbering). Data will be electronically and systematically revalidated after each major change, and corrections/completeness applied whenever necessary.

All system log-ins, interventions, modifications and form status changes will be thoroughly recorded in an Audit Trail log system. Deviations to the protocol will be also tracked and resolution status indicated.

Data and metadata will be exported anonymously in due time in CSV – where required – read into Stata to produce Stata dataset (.dta) files along with associated data dictionary information. Data checking and cleaning will be performed using Stata, and cleaned datasets for use in analyses will be stored in Stata format (Stata version 16). Each step of this process will be monitored through the implementation of individual passwords and regular backups in order to maintain appropriate database access and to guarantee database integrity.

#### **12.2.4 Electronic and central data validation**

Validation/review will be performed in parallel by appropriate people designated by the sponsor-investigator (monitors, data managers, etc.). Up-to-date graphical and text reports, as well as descriptive statistics, will be made available to monitor data in real time. An elaborated electronic process to comment, query and claim correction actions on data via reviewing will reinforce data quality throughout the study conduct and termination. Whenever appropriate, use of controlled vocabulary and common international catalogues (ATC/DCI, MedDRA, NCBI Taxonomy, etc.) will be used.

### **12.3 Monitoring**

The monitoring strategy has been defined as low-risk, according to the SCTO guidelines and the Risk-Based Monitoring (RBM) Score Calculator published on <https://www.sctoplatforms.ch/en/scto-platforms/monitoring-17.html>

A site-initiation visit will be conducted before inclusion of the first participant.

During routine monitoring visits, the verifications will concern:

- Existence and completion of informed-consent forms (100% of the participants)
- Source-data verification for key data (IMP) for 20% of the participants, including first participant
- Trial master file

A close-out visit will be conducted at the end on the study.

### **12.4 Audits and Inspections**

Study documentation, source data/documents and staff will be accessible to auditors/inspectors from the CCER, or any authorised authority as needed; all questions will be answered during inspections. All involved parties will keep participant data strictly confidential.

### **12.5 Confidentiality, Data Protection**

See section 12.2.2 for more detail on data protection. Direct access to source documents will be permitted for the purposes of monitoring (section 12.3), audits and inspections (section 12.4) (ICHE6, 6.10). Sponsor-investigator, investigators, and the data management team will have access to protocol, dataset, statistical code, etc. during and after the study (publication, dissemination).

### **12.6 Storage of biological material and related health data**

Coded samples will be stored independent from the study only with the participant's express consent. All other unused samples will be destroyed at the end of the study.

## **13. PUBLICATION AND DISSEMINATION POLICY**

The trial protocol is registered on ClinicalTrials.gov (NCT05758532) and will be published in a journal once recruitment has started. Dissemination of the findings is planned, regardless of the results, through the WHO, in peer-reviewed journals and at scientific conferences. There will not be any publication restriction. Rule for authorship will follow the ICMJE recommendation.

Sex-subgroup analyses are planned and will be published regardless of the results.

Once the database is cleaned and locked, it will be deposited in a data sharing repository archiving system. Access to the data will follow the rules of the repository system.

## 14. FUNDING AND SUPPORT

### 14.1 Funding

The salary of the PI is first being paid by the University of Geneva, through a position of *Cheffe de Clinique scientifique*, granted by the HUG for the set-up of the proposed project, and then by an *Ambizione* grant from the Swiss National Science Foundation. The study will be funded by the *Ambizione* grant, the grant *Projet de Recherche et Developpement* from the HUG and the *STARTER-MD* grant from the Foundation Louis-Jeantet and the Private Foundation of the HUG. Funders have no role in the design of the study, the analysis of its data, or the decision to publish its results. A copy of the agreements are filed in the TMF.

The study can be simplified in case of insufficient funding. Examples of simplifications include:

- Stopping follow-up after the 9-months visit: the primary outcome analysis would still be possible as it focuses on the period between 6 and 9 months of age.
- Delegation of visits and vaccine administration to treating paediatricians, especially those with no blood sample.
- Simplifying the laboratory experiments, with a reduced number of participants (the minimal required by the sample size calculation).
- Starting with a pilot study (e.g. 60 to 100 participants for clinical outcomes, 20 participants for laboratory outcome) to assess feasibility and verify the assumptions made in the sample size calculation.

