## 4.4 Safety Objectives

### Stage A

**AIM10:** Determine the safety of early MMR vaccination.

*Hypothesis:* MMR vaccine is safe and well-tolerated at 6 months of age, inducing similar safety profile than when given later on.

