### 5.4 Safety Outcomes

**AIM10: Vaccine safety:** occurrence and severity of local and systemic adverse events, as well as any serious adverse events, by systemic organ class, preferred term, severity using toxicity grading scale, and relationship to the intervention from day 0 to day 42 post MMR.

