#### 9.2.4.1 Adverse events

All adverse events, both solicited and unsolicited, will be recorded through day 42 after vaccination. For each adverse event, date and time of onset, duration, resolution, action taken, assessment of intensity/severity (Table 6) and relationship with study treatment will be recorded in REDCap.

Solicited adverse events, will be collected through day 42. They include the following:

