### 9.3.3 Visit 2: Follow-up, 9 months of age ( $t_{+3m} \pm 2$ weeks)

**Review of the fortnightly questionnaires** by investigators, together with the parent, to ensure concordance and the absence of missing data; instruction to continue to fill them every 2 weeks until the subject is 24 months old.

**Review of vaccine diary**, by investigators, together with the parent, to ensure concordance and the absence of missing data; instruction to fill a second vaccine diary the next 42 days.

**Review of vaccination records**, by investigators, to ensure that all is in order. Review with the parent the vaccination plan and ensure it is well understood.

**Overview of the next steps of the trial** by investigators, using the study flow chart to ensure correct comprehension of the parent, with the possibility for parents to ask any question.

**Target clinical examination** will be performed if needed, to ensure that there is no temporary contra-indication for the vaccination (e.g. if the child is sick, the vaccination can be delayed a few days until the illness resolves) or for the blood test (e.g. if the child is sick or recovering, the visit can be delayed a few days until the illness resolves, as it might influence the laboratory test).

**Eczema assessment** will be performed, using SCORAD score.

**Part 2 only: blood will be collected** (maximum 15 ml), in subjects whose parent accept blood collection, for the laboratory tests listed in section 9.2.2. In the eventuality that the blood collection fails or if parents does not accept blood collection at this visit, the subject will remain in Part 2, as they have already provided a baseline blood and further blood collection might succeed.

**Group C.M. or C.C. only: MMR vaccination (first dose)**; Subject randomised to the Group C.M. or C.C. (current schedule for the 1st MMR dose) will receive one dose of MMR vaccine. After reconstitution of the vaccine by adding the entire content of the pre-filled syringe of solvent to the vial containing the powder, the vaccine (0.5 ml) will be injected intramuscularly in the deltoid region or in the anterolateral area of the thigh. The subject will be distracted during the injection, in order to minimise the pain. The subject will remain under close observation for 20 minutes after the injection.

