### 11.2 Determination of Sample Size

The sample size calculation for the clinical outcome (500 participants) is based on the primary outcome of respiratory infections. Based on the data from a previous trial, we expect a rate of respiratory infection of 0.29 episodes per month (SD 0.32) between 6 and 9 months of age in the control groups (Group C.M. or C.C.). By randomising 500 participants, we will have an 80% power to detect a minimum of 30% reduction in this incidence with a 2-sided p-value of 0.05, assuming at least 85% completion rate of the 9 months questionnaire. The 500 participants will be randomised into 4 groups of similar size (see Section 6 and table 3 in Section 8.1): for the primary outcome analysis, the 250 children receiving early MMR at 6 months of age (Group M.C. or M.M.) will be compared with the 250 children receiving the regular MMR at 9 months of age (Group C.M. or C.C.).

		Timing of the 2 nd MMR		
		2 nd MMR 1m after the 12y DPT-PCV (Modified)	2 nd MMR concomitant to the 12y DPT-PCV (Current)	
Primary outcome comparing the timing of the 1 st MMR	1 st MMR at 6m (Modified)	Group M.M., n=125	Group M.C., n=125	N=250
	1 st MMR at 9m (Current)	Group C.M., n=125	Group C.C., n=125	N=250
		N=250	N=250	

Table 7. Participant allocation in 4 groups; for the primary outcome analysis, the Groups M.C. and M.M. will be compared with the Groups C.M. and C.C. C: current MMR schedule; DTP: diphtheria-tetanus-pertussis vaccine; m: month; M: Modified MMR schedule; PCV: pneumococcal conjugate vaccine.

The sample size calculation for the laboratory outcomes (100 participants) is more conservative as it depends on the success of the blood collection and of the laboratory processing for each of the time points. The use of paired samples (taken from the same infant at different ages) reduces the effect of inter-individual heterogeneity and provides greater statistical power with lower participant numbers.

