#### 11.4.2 Primary Analysis

This will be a classic 2-arm trial with regard to the first intervention (early 1st dose of MMR) and the primary outcome (number of respiratory infections between 6 and 9 months of age). The analysis of the

primary outcome will be performed by means of a regression model (either logistic, if the primary outcome is dichotomised as 0 vs  $\geq 1$ , or negative binomial, if numbers of infection episodes are left uncategorized) and will compare the two group of 1st MMR timing (Group M.C. or M.M. vs. Group C.M. or C.C.). The model will be adjusted for sex (male/female), day-care attendance (yes/no), presence of comorbidities (yes/no), older siblings (yes/no), and will be presented as adjusted odd ratios, hazard ratio, or incidence rate ratios (aIRRs) with 95% confidence interval, according to the model chosen.

It will be done in collaboration with the Clinical Research Center at Geneva University Hospitals, once all participants have attended the 9 months visit.

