#### 11.4.5 Safety analysis

AE and SAE will be reported by group, using standard descriptive statistics (frequencies, medians and interquartile ranges, or means and standard deviation) for each AE of interest (see section 10)

- prevalence
- day of onset
- size (e.g. for redness or induration)
- duration
- severity (using standardised grading scales)
- causality with the intervention
- treatment
- resolution

The analyses will be done thrice, in collaboration with the Clinical Research Center at Geneva University Hospitals, at the same time of the interim analysis, the same time of the primary analysis, the same time of the final analysis.

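### The low-funding option of ending follow-up after the 9-month visit would drop the promised 42-day safety window for the comparator groups, whose first MMR is given at that visit

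*Protocol*

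**What the plan says.** Section 14.1 (Funding) allows the study to be simplified if funding is insufficient. Its first example is "Stopping follow-up after the 9-months visit: the primary outcome analysis would still be possible", justified by the primary outcome covering only 6 to 9 months of age. Neither the safety outcome nor the vaccine diary is mentioned.

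Elsewhere the protocol ties safety follow-up to each MMR dose:

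- Section 5.4 defines the AIM10 outcome as the occurrence, severity and "relationship to the intervention from day 0 to day 42 post MMR".
- Section 9.2.4.1 states: "All adverse events, both solicited and unsolicited, will be recorded through day 42 after vaccination".
- Section 9.3.3 (Visit 2, 9 months) states: "Subject randomised to the Group C.M. or C.C. (current schedule for the 1 st MMR dose) will receive one dose of MMR vaccine". At the same visit parents are told to complete a second 42-day diary.
- Section 4.4 gives the AIM10 hypothesis that MMR at 6 months is safe and well tolerated, "inducing similar safety profile than when given later on".
- Section 11.2 gives the size of the group concerned: "the 250 children receiving the regular MMR at 9 months of age".

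On timing, section 11.4.4 places the interim safety analysis after the first 250 randomised children have reached the 9-month visit. Section 11.4.5 repeats the safety analysis at "the same time of the primary analysis", which section 11.4.2 schedules "once all participants have attended the 9 months visit", and again at the final analysis after the 24-month visits.

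**The concern.** One visit has two roles. For the primary outcome it closes the observation period. For Groups C.M. and C.C. it opens the safety window, because the first MMR is given there. Section 14.1 considers only the first role.

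If the option were used as worded, children vaccinated at a study visit would go without the adverse-event follow-up the protocol promises. The trial would also lose its only later first dose. The same stop removes the second-dose visit at 12 or 13 months, so no later-dose safety data would remain for the comparison in section 4.4. A shortage of funds is not a remote case here: the schedule footnotes and sections 6.1.5, 9.3.4 and 14.1 all provide for it.

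The timing of the first two safety analyses raises a smaller version of the same issue. Both are triggered by the 9-month visit, when every 6-month-dose window has closed but the most recent 9-month-dose windows have not.

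**Working it through.** **The figure of 250.** Section 11.2 gives a control rate of 0.29 per month, SD 0.32, a 30% reduction, two-sided 0.05, 80% power and 85% completion.

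- Difference: 0.30 × 0.29 = 0.087.
- Per group: 2 × (1.960 + 0.842)² × 0.32² / 0.087² = 212.4, rounded up to 213.
- With 85% completion: 213 / 0.85 = 250.6, or 251 per group and 502 in total, against 500 stated.

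The planned size reproduces. It matters here only as the number of children in the comparator groups.

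**Windows if follow-up ends at the 9-month visit.** A month is taken as 30.44 days.

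- Early groups (M.C., M.M.): Visit 1 to Visit 2 is 3 × 30.44 = 91 days. With ±2 weeks at each visit the shortest gap is 91 − 28 = 63 days. Since 63 > 42, every window is closed before the stop.
- Comparator groups (C.M., C.C.): the dose is given at Visit 2, so 0 of the 42 days after it are observed for each child under the stop. The maximum is 250 children, if the stop applies to all.

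**Windows at the early safety analyses in the full trial.** Two assumptions are needed: even recruitment of 500 children over the 18 months in section 6.4, and data frozen on the trigger day. The protocol states no such freeze.

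- Recruitment: 500 / 18 = 27.8 per month, of whom 13.9 are comparator children.
- Window: 42 / 30.44 = 1.38 months.
- Comparator children still inside the window: 13.9 × 1.38 = 19.2.
- Interim, about 125 comparator children: 19.2 / 125 = 15%. Primary-time analysis: 19.2 / 250 = 8%.
- A simulation with ±2 weeks of variation in the Visit 1 to Visit 2 interval gives about 16 children at each analysis: 16 / 125 = 13% and 16 / 250 = 6%.
- Those affected miss 21 days on average. That is 402 of 125 × 42 = 5,250 window days at the interim (about 8%) and 402 of 10,500 at the primary-time analysis (about 4%).
- If recruitment took 12 to 30 months instead, the count would run from about 29 down to about 11.
- Final analysis: none, since all 9-month-dose windows closed long before the 24-month visits.

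**The case against.** The best defence is that section 14.1 is being read too harshly. It gives conditional examples, says after the visit rather than at it, and does not cancel the diary. Section 9.2.4.1 requires recording through day 42 without condition. Parents complete the diary online (section 12.1.1), so no further visit is needed. Section 10.1 extends serious adverse event collection through a safety follow-up period, and a substantial amendment would need ethics approval.

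Part of this stands. The option may never be used, and a careful team would probably let the diary run. But the text does not say so. The follow-up period in section 10.1 has no stated length, is attached to serious events, and does not secure the solicited-event diary on which AIM10 relies. Section 14.1 argues that the stop is acceptable without testing it against the safety outcome.

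Three stronger readings are tempting, and the documents do not support them.

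- A reader might infer that AIM10 becomes unanswerable. The objective in section 4.4 is the safety of early MMR, and the later dose enters through the hypothesis. The 6-month-dose windows would be complete. The Visit 1 diary instruction in section 9.3.2 is not limited to vaccinated children, so unvaccinated controls might also supply a concurrent comparison.
- A reader might infer that the 9-month visit is a safety data cut-off. Sections 11.4.2 and 11.4.4 set the earliest time for an analysis, not a cut for each child. On even accrual, child 250 is randomised at about month 9 and reaches the visit at about month 12, while the next DSMB meeting in section 1.6 is at month 18. Nothing forces a freeze at the trigger.
- A reader might infer that the safety comparison is biased against the early dose. That requires unfinished windows to be counted as event-free, which no section says. Section 11.4.5 is descriptive, section 11.5 has missing data marked as such in interim analyses, and the final analysis recovers every window in the full trial.

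**Conclusion.** The point holds for section 14.1. Taken literally, the low-funding stop removes the whole day 0 to 42 window after the first MMR for every comparator child to whom it applies, up to 250, while leaving all early-group windows intact. This conflicts with sections 5.4, 9.2.4.1 and 9.3.3 and removes the later first-dose comparison in the AIM10 hypothesis. It is conditional on the option being used and read as written. It does not prevent a description of the safety of the 6-month dose, and it does not touch the sample size or the primary analysis.

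The analysis-timing point is secondary and minor. Under even 18-month accrual and a freeze on the trigger day, about 16 to 19 comparator children would have incomplete windows: 13 to 15% of about 125 at the interim, and 6 to 8% of 250 at the primary-time analysis. In the full trial the final safety analysis is unaffected.

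**What to change.** Reconcile section 14.1 with sections 5.4, 9.2.4.1 and 9.3.3. It should state that any shortened follow-up ends only after the 42-day diary and the serious adverse event collection following the 9-month dose are complete. This takes one sentence. In the low-funding variant it keeps one online diary that Visit 2 already issues.

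For the secondary point, add to sections 11.4.4 and 11.4.5 that safety data are taken 42 days after the last relevant 9-month visit, or that only completed windows are tabulated, with the number still open shown. The first choice delays those safety tables by about six weeks. The second avoids the delay but leaves the most recent children for a later report. The efficacy timetable, sample size and significance level stay as they are.

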### 14.2 Other Support

Should this be needed, some of the laboratory expenses will be covered by research funds from the Center of Vaccinology, Department of Pathology and Immunology, Faculty of Medicine of Geneva ([name]), and the Infectious Diseases Group at the Murdoch Children's Research Institute, Melbourne, Australia ([name]).

